Brain Imaging	Participants with a	history of	brain metastas	sis should h	ave surveillance MRI as clinically indicated at the discretion of the investigator. See Section 9.4.1 .					
Other: Bone Scan			As c	linically inc	licated per local standards. See Section 9.4.1.					
Clinical Supplies										
IRT Assignment	X				Once eligibility has been confirmed, IRT assignment may be performed up to 3 days prior to study drug administration.					
Study Drug Adm	inistration				Details regarding preparation and administration are provided in the pharmacy manual or training materials.					

Abbreviations: C, Cycle; CT, computed tomography; d, days; D, Day; ECG, electrocardiogram; ECOG, Eastern Cooperative Oncology Group; EDC, Electronic Data Capture; EOI, end of infusion; EOT, end of treatment; hCG, human chorionic gonadotropin; IRT, Interactive Response Technologies; MRI, magnetic resonance imaging; PK, pharmacokinetic(s); SAE, serious adverse event; T3, triiodothyronine; T4, thyroxine; TSH, thyroid stimulating hormone; WOCBP, women of childbearing potential.

Protocol Amendment No.: 07

<sup>a For participants who complete all scheduled cycles of therapy, the EOT visit will be the same visit as the last scheduled and completed on-treatment visit and the start of the Week 1 Clinical/Safety Follow-up visit.

Protocol Amendment No.: 07

b For participants who do not complete all scheduled cycles of therapy, the EOT visit will be the next visit following the last study dose. If the EOT visit occurs 30 days or more after receipt of the last dose, then the EOT visit and Follow-up 1 visit can be completed at the same time.

<sup>c If multiple procedures are required at a single timepoint, safety assessments (ECGs, vital signs, and pulse oximetry) are a higher priority than PK/immunogenicity sampling.

Table 2-6: On-treatment Procedural Outline (Part 1C and Part 2 - BMS-986253 Q2W and Nivolumab and Ipilimumab Q3W)

Cycle 1 and 2 (42 d) Cycle 3 and Beyond (28 d)		EOT a,b	Notes								
	D1	D15	D22	D29	D36	DI	D15				
Safety Assessmen	Safety Assessments c										
Vital Signs and Oxygen Saturations	X	X	X	X		X		X	Includes body temperature, respiratory rate, seated blood pressure, and heart rate. Blood pressure and heart rate should be measured after the participant has been resting quietly for at least 5 minutes. Consider alternate position(s) for vital sign collection. Obtain oxygen saturation at rest. *Pre- and post-dose vital signs on Day 1 of each cycle. Note: Post dose vital signs are to be taken after nivolumab infusion, ipilimumab infusion and BMS-986253 or placebo infusion.		
Weight	X		X			X		X			
Physical Examination (Complete)	X		X			X		X	Physical Examination (Complete)		
ECOG Performance Status	X		X			X			Appendix 5		
Concomitant Medication Assessments	X	X	X	X		X		X	Assess concomitant treatment during the study duration.		

Table 2-6: On-treatment Procedural Outline (Part 1C and Part 2 - BMS-986253 Q2W and Nivolumab and Ipilimumab Q3W)

Procedure			cle 1 ar (42 d)			Bey	3 and rond 3 d)	EOT a,b	Notes
	D1	D15	D22	D29	D36	D1	D15		
ECG	X		X*			х		X	Participants with no clinically relevant changes on ECGs at 6 months on treatment may discontinue routine ECGs.  See of ECGs.  * Required for Part 1C only.
Laboratory Testing	X		X			X		X	See Section 9.1.4  Only applicable for Part 1C: For HCC participants AFP
Pregnancy Test (WOCBP)	X					X		X	Serum or urine pregnancy test must be performed (urine pregnancy test: minimum sensitivity 25 IU/L or equivalent units of hCG) within 24 hours prior to administration of study drug.
Thyroid Function Tests (TSH)	X		X			X*			*TSH to be done on C3D1, C4D1, C5D1, and C6D1. TSH to be done every other cycle, after C6D1 (ie, C8D1, C10D1, etc). If TSH is abnormal, T3 and free T4 should be collected. Results should be examined by the investigator or appropriate designee within 48 hours of dose administration.

Date: 17-May-2024

Approved v 8.0 930120018 9.0

Table 2-6: On-treatment Procedural Outline (Part 1C and Part 2 - BMS-986253 Q2W and Nivolumab and Ipilimumab Q3W)

Procedure	Cycle 1 and 2 (42 d)  Cycle 3 and Beyond (28 d)  EOT a,b Notes					Notes					
	D1	D15	D22	D29	D36	D1	D15				
Adverse Event Ro	portin	g									
Monitor for Nonserious Adverse Events		All nonserious adverse events must be collected starting with the first dose of study drug and for a minimum of 100 days after discontinuing study treatment.									
Monitor for Serious Adverse Events	All SAEs must be collected from the date of participant's written consent and for a minimum of 100 days after discontinuing study treatment. Death due to disease progression within 100 days of discontinuation of study treatment must be reported as an SAE.										
Other Assessmen	ts										
PK Assessments								See Section	9.5 for further details		
Immunogenicity Assessments								See Section	9.5 for further details		
Biomarker Assessments								Se	e Section 9.8		
Additional Research Sampling		See Section 9.8.4									
Efficacy Assessments								Se	e Section 9.4		
Body Imaging									n, pelvis, and all other known/suspected sites of disease should occur every ks, then every 12 weeks (± 7 days) until withdrawal of consent, death, o		

Date: 17-May-2024

Approved v8.0 930120018 9.0

Table 2-6: On-treatment Procedural Outline (Part 1C and Part 2 - BMS-986253 Q2W and Nivolumab and Ipilimumab Q3W)

Cycle 1 and 2 (42 d)  Beyond (28 d)  Cycle 3 and Beyond (28 d)  Notes						Notes					
	D1	D15	D22	D29	D36	D1	D15				
		itiation of another anti-cancer treatment, whichever occurs first. For HCC participants, contrast-enhanced triphasic CT of the liver is equired. See Section 9.4.1.									
	abdor 48 we	For Part 2: Timing of scans should be based on date of first treatment, which is considered Week 1. Contrast-enhanced CT/MRI of the chest, abdomen, pelvis, and all other known/suspected sites of disease should occur every 8 weeks (± 7 days), starting from first dose for the first 48 weeks, then every 12 weeks (± 7 days). Tumor assessments should continue until BICR-confirmed disease progression, final analysis, or treatment discontinuation (including treatment beyond progression), whichever occurs later. See Section 9.4.1.									
Brain Imaging	Parti	Participants with a history of brain metastasis should have surveillance MRI as clinically indicated at the discretion of the investigator. See Section 9.4.1.									
Other: Bone Scan						A	s clinica	ally indicated pe	er local standards. See Section 9.4.1.		
Clinical Supplies											
IRT Assignment	X								Once eligibility has been confirmed, IRT assignment may be performed up to 3 days prior to study drug administration.		
Study Drug Admi	inistrat	tion									
Nivolumab Administration	X		X			X			Nivolumab will be administered every 3 weeks for the first 2 cycles (4 doses) and then every 4 weeks for Cycle 3 and beyond. See Section 7.1 for nivolumab dose administration.		
Ipilimumab Administration	X		X						Ipilimumab will be administered every 3 weeks on Cycles 1 and 2 (4 doses) ONLY. See Section 7.1 for ipilimumab dose administration.		

Date: 17-May-2024

Approved v 8.0 930120018 9.0

Abbreviations: AFP, alpha fetoprotein; BICR, blinded independent central review; C, Cycle; CT, computed tomography; d, days; D, day; ECG, electrocardiogram; ECOG, Eastern Cooperative Oncology Group; EDC, Electronic Data Capture; EOT, end of treatment; HCC, hepatocellular carcinoma; hCG, human chorionic gonadotropin; IRT, Interactive Response Technologies; MRI, magnetic resonance imaging; PK, pharmacokinetic(s); QXW, every X weeks; SAE, serious adverse event; T3, triiodothyronine; T4, thyroxine; TSH, thyroid stimulating hormone; WOCBP, women of childbearing potential.

- a For participants who complete all scheduled cycles of therapy, the EOT visit will be the same visit as the last scheduled and completed on-treatment visit and the start of the Week 1 Clinical/Safety Follow-up visit.
- b For participants who do not complete all scheduled cycles of therapy, the EOT visit will be the next visit following the last study dose. If the EOT visit occurs 30 days or more after receipt of the last dose, then the EOT visit and Follow-up 1 visit can be completed at the same time.
- c If multiple procedures are required at a single timepoint, safety assessments (ECGs, vital signs, and pulse oximetry) are a higher priority than PK/immunogenicity sampling.

Protocol Amendment No.: 07

 Table 2-7:
 Safety Follow-up Procedural Outline

	FU 1	FU 3	Response Follow-up	Notes
Procedure	30 Days (± 7 Days)	100 Days (± 7 Days)	(Q12W)	
Safety Assessments				
Concomitant Medications	X	X		
ECOG Performance Status	X	X		Appendix 5
Physical Examination	X	X		
Vital Signs/Oxygen Saturation and Weight	X	X		Including weight, body temperature, respiratory rate, pulse oximetry, seated BP, and heart rate.
Laboratory Tests				
Hematology and Serum Chemistry	X	X		See Section 9.1.4  Only applicable for Part 1C: For HCC participants: AFP
Pregnancy testing (WOCBP)	X	X		
Pharmacokinetic Assessment				
PK / Immunogenicity Sampling	S	ils		
Adverse Event Reporting		AEs reported during this time period should be followed until resolved to baseline, stabilized, or deemed irreversible.		
Monitor for Nonserious AEs	All nonserious adverse even and for a minimum			
Monitor for SAEs	100 days after discontinuing	from the time of signing the c g study treatment. Death due t ntinuation of dosing must be r	o disease progression within	

Table 2-7: Safety Follow-up Procedural Outline

	FU 1	FU 3	Response Follow-up	Notes			
Procedure	30 Days (± 7 Days)	100 Days (± 7 Days)	(Q12W)				
Efficacy Assessments							
New and Subsequent Anti- cancer Therapy	X	X		New anti-cancer therapy including radiotherapy, surgery, and systemic therapy			
Tumor Type Assessment							
Body Imaging	
 
Part 1: See Section 9.4.1. After EOT, participants should continue tumor assessment on the same schedule, every 8 weeks (± 7 days), starting from first dose for the first 48 weeks, then every 12 weeks (± 7 days), until withdrawal of consent, death, initiation of another anti-cancer treatment, final analysis, or for up to a maximum of 2 years, whichever occurs first.
 
Part 2: Timing of scans should be based on date of first treatment, which is considered Week 1.
 
See Section 9.4.1. After EOT, participants in Part 2 will continue to have radiologic and clinical tumor assessments on the same schedule, every 8 weeks (± 7 days), starting from the first dose for the first 48 weeks, then every 12 weeks (± 7 days), until BICR-confirmed disease progression, final analysis, or treatment discontinuation (including treatment beyond progression), whichever occurs later.
 
For participants with SCCHN, a CT or MRI of the neck is required. For HCC participants, contrast-enhanced triphasic CT of the liver is required. See Section 9.4.1 for further details.
 
						
Brain Imaging	See Section 9.4.1. Participants with a history of brain metastasis should have surveillance MRI as clinically indicated at the discretion of the investigator.						
Other Bone Scan		4.1. As clinical indicated per					

Abbreviations: AE, adverse event; AFP, alpha fetoprotein; BICR, blinded independent central review; BP, blood pressure; CT, computed tomography; ECOG, Eastern Cooperative Oncology Group; EOT, end of treatment; FU, follow-up; HCC, hepatocellular carcinoma; IgG, immunoglobulin G; MRI, magnetic resonance imaging; PK, pharmacokinetic(s); Q12W, every 12 weeks; SAE, serious adverse event; SCCHN, squamous cell carcinoma of the head and neck; WOCBP, women of childbearing potential.

Protocol Amendment No.: 07 Date: 17-May-2024

Approved v8.0 930120018 9.0

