#### Follow-up:

• Safety Follow-up Period: Upon completion of study therapy (or up to a maximum of 156 weeks if applicable), or once the decision is made to discontinue the participant from treatment, ie, at end of treatment (EOT), all participants will enter a safety follow-up period. For participants who complete all scheduled cycles of therapy, the EOT visit will be the same visit as the last scheduled and completed on-treatment visit, and will be the start of the safety follow-up period. For participants who do not complete all scheduled cycles of therapy, the EOT visit will be the next visit following the last study dose. If the EOT visit occurs 30 days or more after receipt of the last dose, then the EOT visit and Follow-up 1 visit can be completed at the same time. All participants will be evaluated for any new AEs for a minimum of 100 days after discontinuing study treatment. Follow-up visits should occur at Days 30 and 100 (± 7 days for all study visits) after the last dose. All participants will be required to complete the clinical safety follow-up visits, regardless of whether new anti-cancer therapy is started, except those participants who withdraw consent for study participation.

• Response Follow-up Period: At the time of study treatment discontinuation, participants in Part 1 will continue to have radiologic and clinical tumor assessments on the same schedule, every 8 weeks (± 7 days), for the first 48 weeks after the first dose. After 48 weeks, radiological and clinical tumor assessments will occur every 12 weeks (± 7 days), until withdrawal of consent, death, final analysis, or initiation of another anti-cancer treatment, whichever occurs first, for up to 2 years after EOT. Participants in Part 2 will continue to have radiologic and clinical tumor assessments on the same schedule, every 8 weeks (± 7 days), starting from first dose for the first 48 weeks, then every 12 weeks (± 7 days), until blinded independent central review (BICR)-confirmed disease progression, final analysis, or treatment discontinuation (including treatment beyond progression), whichever occurs later. After the final analysis, radiological assessments will be done per standard of care, at the discretion of the treating physician.

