# 5.1.5.2 Response Follow-up Period

At the time of study treatment discontinuation, participants in Part 1 will continue to have radiologic and clinical tumor assessments on the same schedule, every 8 weeks ( $\pm$  7 days), for the first 48 weeks after the first dose. After 48 weeks, radiological and clinical tumor assessments will occur every 12 weeks ( $\pm$  7 days), until withdrawal of consent, death, or initiation of another anticancer treatment, whichever occurs first, for up to 2 years after EOT.

Participants in Part 2 will continue to have radiologic and clinical tumor assessments on the same schedule, every 8 weeks ( $\pm$  7 days), starting from first dose for the first 48 weeks, then every 12 weeks ( $\pm$  7 days), until blinded independent central review (BICR)-confirmed disease progression, final analysis, or treatment discontinuation (including treatment beyond progression), whichever occurs later.

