## 7.11 Treatment After the End of the Study

At the conclusion of the study, participants who continue to demonstrate clinical benefit may be eligible to receive BMS-supplied study treatment.

Those participants who demonstrate clinical benefit from treatment without unacceptable toxicity may continue treatment beyond the 3-year treatment period, up to a maximum of 5 years from the first dose of study treatment, at the discretion of the investigator and after discussion with the Medical Monitor, until loss of that benefit, unacceptable toxicity, or participant/physician decision to withdraw.

If a participant continues study treatment beyond the 3-year treatment period, procedures during the extended treatment duration will be minimized to clinical and laboratory safety monitoring, AE collections, and tumor assessments every 12 weeks until the final analysis.

BMS reserves the right to terminate access to BMS-supplied study treatment if any of the following occur: a) the study is terminated due to safety concerns; b) the development of BMS-986253 is terminated for other reasons, including but not limited to lack of efficacy and/or not meeting the study objectives; c) the participant can obtain medication from a government-sponsored or private health program. In all cases, BMS will follow local regulations.

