#### 9 STUDY ASSESSMENTS AND PROCEDURES

- Study procedures and timing are summarized in the Schedule of Activities (See Section 2).
- Protocol waivers or exemptions are not allowed.
- All immediate safety concerns must be discussed with the Sponsor immediately upon occurrence or awareness to determine if the participant should continue or discontinue treatment.
- Adherence to the study design requirements, including those specified in the Schedule of Activities, is essential and required for study conduct.
- All screening evaluations must be completed and reviewed to confirm that potential participants meet all eligibility criteria before randomization. The investigator will maintain a screening log to record details of all participants screened and to confirm eligibility or record reasons for screening failure, as applicable.
- Procedures conducted as part of the participant's routine clinical management (eg, blood count) and obtained before signing of informed consent may be utilized for screening or baseline purposes provided the procedure meets the protocol-defined criteria and has been performed within the timeframe defined in the Schedule of Activities.

Additional measures, including non-study required laboratory tests, should be performed as clinically indicated or to comply with local regulations. Laboratory toxicities (eg, suspected druginduced liver injury [DILI] enzyme evaluations) will be monitored during the follow-up phase via on site/local labs until all study treatment related toxicities resolve, return to baseline, or are deemed irreversible.

If a participant shows pulmonary-related signs (hypoxia, fever) or symptoms (eg, dyspnea and cough) consistent with possible pulmonary AEs, the participant should be immediately evaluated

to rule out pulmonary toxicity, according to the suspected pulmonary toxicity management algorithm in the BMS-936558 (nivolumab) IB.

Some of the assessments referred to in this section may not be captured as data in the eCRF. They are intended to be used as safety monitoring by the treating physician.

Additional testing or assessments may be performed as clinically necessary or where required by institutional or local regulations.

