## 9.4 Efficacy Assessments

Following the database lock for the final analysis, efficacy will no longer be assessed. Imaging should be performed per standard of care at the discretion of the treating physician.

Efficacy assessments for the anti-tumor activity of BMS-986253, in combination with nivolumab or in combination with nivolumab and ipilimumab, will use investigator assessed tumor measurements, per RECIST v1.1 (Appendix 8).

Assessments of partial response (PR) and CR must be confirmed at least 4 weeks after initial response. Changes in tumor measurements and tumor responses will be assessed by the investigator per study design using RECIST v1.1 criteria (Appendix 8). Investigators will also report the number and size of new lesions that appear while on study. The timepoint of tumor assessments will be reported on the eCRF based on the investigator's assessment.

A BICR will be utilized in this study for determination of BICR-assessed endpoints. The BICR will review all available tumor assessment scans for all treated participants until the final analysis is completed. Details of BICR responsibilities and procedures will be specified in the BICR charter.

A Best Overall Response of SD requires a minimum of 49 days on study from the date of first dose to the date of the first imaging assessment.

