## 9.4.1 Imaging Assessment for the Study

Following the final analysis, images will no longer be submitted for BICR evaluation. Imaging should be performed per institutional standard of care.

Until final analysis, images will be submitted to an imaging core laboratory and may be reviewed by BICR at any time during the study. Sites should be qualified prior to scanning the first participant and understand the image acquisition guidelines and submission process as outlined in the CA027002 Imaging Manual provided by the core laboratory.

Baseline images should be acquired as outlined in Table 2-2. On-study images should be acquired as outlined in Table 2-3, Table 2-4, and Table 2-5 from the date of first dose. Tumor assessments at other timepoints may be performed if clinically indicated and should be submitted to the central imaging vendor as soon as possible. Unscheduled CT/MRI should be submitted to the central imaging vendor. X-rays and bone scans that clearly demonstrate interval progression of disease, for example most commonly as unequivocal lesions that are unmistakably new since the prior CT/MRI, should be submitted to the central imaging vendor. Otherwise, they do not need to be submitted centrally.

Images will be acquired within 28 days prior to the first treatment dose. Images acquired as part of care prior to signing the ICF, but within the 28-day limit, will be acceptable if there is no intervening treatment, and all required scanning acquisition parameters are met (if feasible per local regulations).

For Part 1: On-treatment images will be acquired every 8 weeks ( $\pm$  7 days) up until Week 48 and then every 12 weeks ( $\pm$  7 days) until withdrawal of consent, death, or initiation of another anticancer treatment, whichever occurs first. For Part 2: On-treatment images will be acquired every 8 weeks ( $\pm$  7 days) up until Week 48 and then every 12 weeks ( $\pm$  7 days) until BICR-confirmed disease progression, or treatment discontinuation (including treatment beyond progression), whichever occurs later.

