## 9.4.2 BICR Confirmation of Progression (Part 2)

Following the final analysis, images will no longer be submitted to BICR for evaluation. Imaging should be performed per institutional standard of care.

Until final analysis, sites should submit all scans to the central imaging vendor on a rolling basis, throughout the duration of the study. BICR of scans will occur on a rolling basis, blinded to treatment arm, clinical data, and investigator assessment of submitted scans. For Part 2, when progression per RECIST 1.1 criteria is assessed by the investigator, the site will inform the central imaging vendor, in order for BICR assessment of progression to be performed. The BICR will be completed and the results provided to the site as specified in the imaging vendor documents, provided there are no pending imaging queries to the site. All details on the timelines and associated process requirements will be outlined in the Imaging Manual.

Participants whose progression is not confirmed by the BICR will be required to continue tumor assessments (if clinically feasible) according to the protocol-specified schedule, or sooner if clinically indicated. Also, if participants discontinue treatment without radiographic progression, tumor assessments will continue according to the protocol-specified schedule, as noted in Section 2 (Schedule of Activities) until progression has been confirmed by BICR.

All study treatment decisions will be based on the investigator's assessment of tumor images and not on the BICR assessment.

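### Do the differing Part 2 imaging stop rules put the response or PFS results at risk?

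*Combined protocol and SAP*

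**What the plan says.** Four places give the Part 2 rule as the latest of three events: BICR-confirmed progression, final analysis and treatment discontinuation. They are the Response Follow-up bullet of the Protocol Summary, the Body Imaging rows of Tables 2-6 and 2-7, and Section 5.1.5.2. Table 2-6 reads "Tumor assessments should continue until BICR-confirmed disease progression, final analysis, or treatment discontinuation (including treatment beyond progression), whichever occurs later", and Section 5.1.5.2 ends its rule with "final analysis, or treatment discontinuation (including treatment beyond progression), whichever occurs later".

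Section 9.4.1 states the Part 2 rule twice, on treatment and after discontinuation. Each time it takes the later of only two events: "disease progression, or treatment discontinuation (including treatment beyond progression), whichever occurs later".

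For a participant who comes off treatment with no progression yet seen on imaging, Section 9.4.2 says: "tumor assessments will continue according to the protocol-specified schedule, as noted in Section 2 (Schedule of Activities) until progression has been confirmed by BICR".

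Other current text treats the final analysis as the end of protocol imaging. In the Summary, the sentence straight after the three-event rule is "After the final analysis, radiological assessments will be done per standard of care, at the discretion of the treating physician". Section 9.4 says "Following the database lock for the final analysis, efficacy will no longer be assessed". Sections 9.4.1 and 9.4.2 both open by ending BICR submission at the final analysis and moving imaging to institutional standard of care. Section 7.11, for treatment beyond three years, provides for "tumor assessments every 12 weeks until the final analysis".

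**The concern.** Read literally, the three-event rule does two odd things. Before the final analysis, it keeps scanning a participant who has BICR-confirmed progression and has stopped treatment, although the stop sentences in Section 9.4.1 would release that person. After the final analysis, it keeps scanning anyone still on treatment or without BICR-confirmed progression, although several passages hand imaging back to the treating physician. Because no images go to BICR after the final analysis, a participant who has not progressed by then could never reach the BICR event, so the rule would have no attainable end.

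Section 9 makes the schedule binding: "Adherence to the study design requirements, including those specified in the Schedule of Activities, is essential and required for study conduct". Sites following different sections could scan for different lengths of time or be recorded as deviating. If the difference reached the scans behind the primary endpoint, BICR-assessed ORR, or behind PFS, it would be a statistical problem and not merely an editorial one.

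**Working it through.** Let P be BICR-confirmed progression, F the final analysis and D treatment discontinuation. The texts give three stop dates:

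- A = max(P, F, D): Summary, Tables 2-6 and 2-7, Section 5.1.5.2.
- B = max(P, D): the two stop sentences in Section 9.4.1.
- C = F: the release text in the Summary, Section 9.4 and the openings of Sections 9.4.1 and 9.4.2.

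**Do the rules differ?** Stop date under each strict ordering, read literally:

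| Ordering | A | B | C |
|---|---|---|---|
| P < D < F | F | D | F |
| D < P < F | F | P | F |
| P < F < D | D | D | F |
| D < F < P | P | P | F |
| F < P < D | D | D | F |
| F < D < P | P | P | F |

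In none of the six orderings do all three agree. When F is last (2 of 6), A = C and B stops earlier. When F is not last (4 of 6), A = B and both run past F.

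**Do they differ on scans that an endpoint uses?** Table 10.3.1-2 cuts best overall response at first progression or subsequent therapy. Duration of response and PFS run to first progression or death, with censoring before subsequent anticancer therapy. Once the final analysis is locked, efficacy is no longer assessed. No stated endpoint therefore needs a scan after min(P, F).

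- A ≥ P and B ≥ P, because P is inside each maximum.
- C = F.
- Section 9.4.2 runs to P for the participants it covers.

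Each stop date is at or after min(P, F). Scheduled scans available to ORR, duration of response and PFS are identical under every version, so the difference is 0. Nothing in the wording depends on treatment arm.

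**How many unused scans are at issue?** Scans fall every 8 weeks to Week 48 and then every 12 weeks: Weeks 8, 16, 24, 32, 40, 48, 60, 72, 84, 96, 108, 120, 132, 144, 156. The timing of the final analysis is not given, so Weeks 52, 78 and 104 after first dose are assumed, as are the progression weeks.

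Before the final analysis, participant off treatment by P, scans after P up to F (required by A, not by B):

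| P | F = 52 | F = 78 | F = 104 |
|---|---|---|---|
| Week 8 | 5 | 7 | 9 |
| Week 16 | 4 | 6 | 8 |
| Week 24 | 3 | 5 | 7 |
| Week 48 | 0 | 2 | 4 |

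For example, P = 8 and F = 52 leaves Weeks 16, 24, 32, 40 and 48, which is 5.

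After the final analysis, participant treated to Week 156 (the maximum in Section 5.1.5.1), literal reading of A or B: Weeks 60–156 = 9 for F = 52, Weeks 84–156 = 7 for F = 78, Weeks 108–156 = 5 for F = 104. Under C the count is 0.

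**Would a site reach the second set of counts?** The Part 2 Body Imaging entries in Tables 2-6 and 2-7 both refer to Section 9.4.1, which opens with the release to standard of care. Table 2-6 also sends efficacy assessments to Section 9.4, which carries the same release. The Summary gives it in the sentence after the rule. Only Section 5.1.5.2 has neither the release nor a pointer to it.

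**The case for a change.** The strongest case for acting is that the schedule is binding, the three-event wording sits in the schedule itself, and Section 5.1.5.2 repeats it without relief. In the same Table 2-7 row, the Part 1 rule uses the final analysis as a cap (the first of several events), while Part 2 uses it as a floor. That looks like a slip. The release text deals with the period after the final analysis but does nothing for a progressed, off-treatment participant before it, and correcting the wording would cost little.

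The mismatch before the final analysis does stand, as does the missing release in Section 5.1.5.2. The rest is weaker. A clause written specifically for the period after the final analysis is naturally read as overriding the general schedule, so the 9, 7 or 5 later scans arise only if a site ignores the section its table names. The Section 9.4.2 sentence covers only participants who stop without radiographic progression, and it defers to the schedule. Section 7.11 is a special provision for treatment beyond three years. The counts starting at Week 8 also suppose that the present wording governed those visits. Amendment 07, dated 17-May-2024, introduced the final-analysis imaging changes when Part 2 participants were already enrolled, and the wording that governed earlier visits is not available. Death and withdrawal of consent are ignored as well.

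One point cannot be closed from the documents: some exploratory Part 2 endpoints are not visible, so their use of scans after progression cannot be judged.

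**Conclusion.** This is a clerical inconsistency in an operational rule, and it calls for no change to the plan. The passages do give different stop dates, but every version images through the earlier of BICR-confirmed progression and the final analysis, and the stated definitions of ORR, duration of response and PFS use nothing later. The effect on those endpoints is nil. The residual is possible extra scanning before the final analysis for participants who have progressed and stopped treatment: between 0 and 9 scans each under the assumed dates, as an upper bound. After the final analysis, the release text and the cross-references to it already give sites a workable answer. Aligning the wording would change no estimate, test or analysis set.

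The conclusion rests on the endpoint definitions in Table 10.3.1-2, on the end of BICR submission at the final analysis, and on the specific release text prevailing over the general schedule. It does not extend to exploratory endpoints that cannot be seen.
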